22. The subject has a resting heart rate outside of the range of 40 to 100 beats per minute, confirmed on repeat testing within a maximum of 30 minutes, at Screening Visit or Check-in (Day -1) of Period 1 or 2.
23. The subject has abnormal clinical laboratory test values that suggest a clinically significant underlying disease or has ALT and/or AST >1.5×ULN at Screening or Check-in (Day -1) of Period 1 or 2.
24. The subject has any dietary restrictions or preferences that may interfere with the conduct of the study.

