7.5 Criteria for Discontinuation or Withdrawal of a Subject

The primary reason for discontinuation or withdrawal of the subject from the study or study drug should be recorded in the eCRF using the following categories. For screen failure subjects, refer to [Section 9.1.17](#).

1. Pretreatment event (PTE) or AE. The subject has experienced a PTE or AE that requires early termination because continued participation imposes an unacceptable risk to the subject's health or the subject is unwilling to continue because of the PTE or AE.

- Liver Function Test (LFT) Abnormalities

Study drug should be discontinued immediately with appropriate clinical follow-up (including repeat laboratory tests, until a subject's laboratory profile has returned to normal/baseline status, see [Section 9.1.8](#)), if the following circumstances occur at any time during study drug treatment:

- ALT or AST $>8 \times$ ULN, or
- ALT or AST $>5 \times$ ULN and persists for >2 weeks or based on clinical judgment of the investigator, or

- ALT or AST $>3\times$ ULN in conjunction with elevated total bilirubin $>2\times$ ULN or INR >1.5 , or
 - ALT or AST $>3\times$ ULN with appearance of fatigue, nausea, vomiting, right upper quadrant pain or tenderness, fever, rash, and/or eosinophilia ($>5\%$).
2. Significant protocol deviation. The discovery postrandomization that the subject failed to meet protocol entry criteria or did not adhere to protocol requirements, and continued participation poses an unacceptable risk to the subject's health.
 3. Lost to follow-up. The subject did not return to the clinic and attempts to contact the subject were unsuccessful. Attempts to contact the subject must be documented in the subject's source documentation.
 4. Voluntary withdrawal. The subject (or subject's legally acceptable representative) wishes to withdraw from the study. The reason for withdrawal, if provided, should be recorded in the eCRF.

Note: All attempts should be made to determine the underlying reason for the withdrawal and, where possible, the primary underlying reason should be recorded (ie, withdrawal because of an AE should not be recorded in the "voluntary withdrawal" category).

5. Study termination. The sponsor, IRB, or regulatory agency terminates the study.
6. Pregnancy. The subject is found to be pregnant.
Note: If the subject is found to be pregnant, the subject must be withdrawn immediately. The procedure is described in Section 9.1.10.

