9.1.8 Procedures for Clinical Laboratory Samples

All samples will be collected in accordance with acceptable laboratory procedures. Laboratory samples will be collected following an overnight fast of ≥ 10 hours (except for those collected at Screening) on the days stipulated in the Schedule of Study Procedures in [Appendix A](#).

The tests that will be performed for each clinical laboratory specimen are listed in [Table 9.a](#).

Table 9.a Clinical Laboratory Tests

Hematology	Serum Chemistry	Urinalysis
RBCs	ALT	pH
WBCs with differential (% and absolute)	Albumin	Specific gravity
Hemoglobin	Alkaline phosphatase	Protein
Hematocrit	AST	Glucose
Platelets	Total bilirubin	Blood
Prothrombin time/INR	Direct bilirubin	Nitrite
aPTT	Total protein	
	Creatinine	Microscopic Analysis: (a)
	Blood urea nitrogen	RBC/high power field
	Creatine kinase	WBC/high power field
	GGT	Epithelial cells, casts, etc
	Potassium	
	Sodium	
	Glucose	
	Chloride	
	Bicarbonate	
	Calcium	

Diagnostic Screening:

Serum

HIV (b)
 HBsAg and anti-HCV (b)
Female subjects only:
 hCG (for pregnancy) (d)
 FSH (b) (e)

Urine

Drug screen including amphetamines, barbiturates, benzodiazepines, cannabinoids, cocaine, opiates, alcohol, and cotinine (c)

aPTT=activated partial thromboplastin time, FSH=follicle-stimulating hormone, GGT= γ -glutamyl transferase, hCG=human chorionic gonadotropin, RBC=red blood cell, WBC=white blood cell.

- (a) Microscopic examination of sediment to be performed only if the dipstick results are positive.
- (b) To be performed at Screening only.
- (c) To be performed at Screening and Check-in (Day -1) of Periods 1 and 2.
- (d) To be performed at Screening, Check-in (Day -1) of Period 1, and Study Exit/Early Termination.
- (e) For female subjects when menopause is suspected and subject is not surgically sterile.

The local laboratory will perform laboratory tests for hematology, serum chemistry, and urinalysis. The results of laboratory tests will be returned to the investigator, who is responsible for reviewing and filing these results.

If subjects experience ALT or AST $>3\times$ ULN, follow-up laboratory tests (at a minimum, serum alkaline phosphatase, ALT, AST, total bilirubin, GGT, and INR) should be performed preferably within 48 to 72 hours and no later than 7 days after the abnormality was noted (please refer to Section 7.5 for discontinuation criteria and Section 10.2.3 for reporting requirements related to abnormal LFT results).

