If the ALT or AST remains elevated $>3\times$ ULN on these 2 consecutive occasions, the investigator must contact the Medical Monitor for consideration of additional testing, close monitoring, possible discontinuation of study drug, discussion of the relevant subject details and possible alternative etiologies. The abnormality should be recorded as an AE (please refer to Section 10.2.3 for reporting requirements related to abnormal LFT results).

The investigator or designee is responsible for transcribing or attaching laboratory results to the eCRF. The investigator will maintain a copy of the laboratory accreditation and the reference ranges for the laboratory used.

Laboratory reports must be signed and dated by the principal investigator indicating that the report has been reviewed and any abnormalities have been assessed for clinical significance. Any abnormalities identified prior to the first dose of study drug will require clear and complete documentation in the source documents as to the investigator's assessment of not clinically significant before proceeding with enrollment or randomization.

All clinically significant laboratory abnormalities must be recorded as a PTE/AE in the subject's source documents and on the appropriate eCRF. A clinically significant laboratory abnormality that has been verified by retesting will be followed until the abnormality returns to an acceptable level or a satisfactory explanation has been obtained.

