14.2 Protocol Deviations

The investigator should not deviate from the protocol, except where necessary to eliminate an immediate hazard to study subjects. Should other unexpected circumstances arise that will require deviation from protocol-specified procedures, the investigator should consult with the sponsor or designee (and IRB, as required) to determine the appropriate course of action. There will be no exemptions (a prospectively approved deviation) from the inclusion or exclusion criteria.

The site should document all protocol deviations in the subject's source documents, where applicable. In the event of a significant deviation, the site should notify the sponsor or its designee (and IRB, as required). Significant deviations include, but are not limited to, those that involve fraud or misconduct, increase the health risk to the subject, or confound interpretation of primary study assessment. A Protocol Deviation Form should be completed by the site and signed by the sponsor or designee for any significant deviation from the protocol.

The investigator should document all protocol deviations.

Every attempt will be made to collect each PK and PD blood sample at the designated time point, and the actual time of each blood sample will be recorded on the source document and eCRF. Blood samples not collected within the window specified for the scheduled sample time should be reported to Takeda using the Protocol Deviation Form. Protocol Deviation Forms are to be completed for PK/PD samples collected outside of the windows defined in [Table 14.a](#).

Table 14.a Windows for PK and PD Blood Sample Collection

Minutes	Nominal Sampling Time
≤30 minutes predose	0 hour
±5	immediately postdose to ≤6 hours
±10	>6 hours to ≤12 hours postdose
±15	>12 hours to ≤24 hours
±30	>24 hours

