Appendix A Schedule of Study Procedures

Period Day	Screening	Treatment Period 1						Treatment Period 2						ET (a)	Follow-up (b)	
	-28 to -2	-1 (Period 1 Check-in)	1	2	3	4	6	8/-1 (Period 2 Check-in)	1	2	3	4	6			8 (Study Exit)
Study Day	-28 to -2	-1	1	2	3	4	6	8	9	10	11	12	14	16		23 (±2)
Informed consent	X															
Inclusion/exclusion criteria	X	X														
Demographics, medical history	X															
Medication history	X															
Physical examination	X	X												X	X	
Vital signs (c)	X	X	X (d)	X	X	X	X	X	X (d)	X	X	X	X	X	X	X
Weight, height, BMI (e)	X	X												X	X	
Concomitant medications (f)	X	X	X	X	X	X	X	X	X	X	X	X	X	X	X	X
Concurrent medical conditions	X	X														
Clinical laboratory tests (g)	X	X			X (h)			X (i)			X (h)			X	X	
HBsAg, anti-HCV, HIV	X															
FSH (j)	X															
Pregnancy test (hCG) (k)	X	X												X	X	
Urine drug screen	X	X						X								
C-SSRS	X	X												X	X	
ECG	X	X	X (l)					X	X (l)					X	X	
DNA sample collection (m)			X													
PK blood collection (n)			X	X	X	X			X	X	X	X				
CCI																
Dispense study drug			X						X							
Confinement		X	X	X	X			X	X	X	X					
PTE assessment (p)	X	X	X													
AE assessment (q)			X	X	X	X	X	X	X	X	X	X	X	X	X	X

Footnotes for Appendix A are on the next page.

Footnotes for Appendix A:

ET=Early Termination.

- (a) Procedures to be performed for subjects who prematurely discontinue the study.
- (b) The Follow-up Visit will occur (14 days after the last dose of study drug) by telephone unless abnormal, clinically significant findings were observed at Study Exit. In these cases, subjects will be brought back into the clinic for re-evaluation at the investigator's discretion.
- (c) Vital signs will include oral body temperature, respiratory rate, blood pressure, and heart rate (beats per minute). Blood pressure and heart rate will be measured in 2 positions: after 5 minutes supine and then after 1 and 3 minutes standing.
- (d) Vital signs will be measured at predose (within 50 minutes before dosing) and at 1, 4, and 12 hours postdose.
- (e) Height and BMI only will be collected at Screening.
- (f) All concomitant medications taken from Screening and throughout the study will be recorded.
- (g) Hematology, serum chemistry, and urinalysis.
- (h) Blood and urine samples for clinical laboratory tests will be collected on rising.
- (i) Only 1 blood sample will be collected on this day that will serve as the Period 2 Day -1 sample.

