### 7.12.2 Clinical Laboratory Evaluations

Clinical safety laboratory tests include clinical chemistry, hematology, and urinalysis. The samples for these tests are collected at Screening, Check-in Period 1, Day 3 Period 1, Check-in

Period 2 (Day -1 of Period 2; also Day 8 of Period 1), and Day 3 Period 2 and Study Exit (Day 8 of Period 2 or Early Termination).

Descriptive statistics (N, mean, median, SD, minimum and maximum) of clinical laboratory tests will be summarized for baseline, post dose (Days 3 and 8), and change from baseline to post dose by regimen. The Baseline for each regimen is defined as the last observation prior to the dose of study drug in the corresponding period. Only the scheduled measurements will be included in the summary. No statistical tests will be performed.

Individual results for clinical laboratory test will be evaluated against the Takeda predefined laboratory markedly abnormal values (MAV) criteria ([Appendix A](#)) using the result and criteria in SI units. All subjects with at least 1 post dose laboratory result that meets the MAV criteria will be presented in a data listing. The number and percentage of subjects with at least 1 post dose markedly abnormal laboratory test result will also be summarized by regimen. Subjects who meet the MAV criteria will be mapped to their respective qualifying laboratory result. All post dose clinical lab MAV results, including scheduled and unscheduled measurements will be included in the MAV summaries.

All clinical laboratory data will be presented in both SI and conventional units in data listings.

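### Do the ALT/AST limit at Period 2 Check-in and the liver stopping limits give conflicting answers on the second dose?

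*Protocol*

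**What the plan says.** **The check at Period 2 Check-in.** Protocol 7.2 item 23 excludes a subject with "ALT and/or AST >1.5×ULN at Screening or Check-in (Day -1) of Period 1 or 2". Protocol 14.2 adds: "There will be no exemptions (a prospectively approved deviation) from the inclusion or exclusion criteria".

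**The sample.** In Appendix A, Period 2 Check-in falls on Study Day 8, which is also Day 8 of Period 1. Footnote (i) says: "Only 1 blood sample will be collected on this day that will serve as the Period 2 Day -1 sample". SAP 7.12.2 treats the two visits as one in the same way.

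**The stopping limits.** Protocol 7.5 item 1 says "Study drug should be discontinued immediately with appropriate clinical follow-up" if any of four conditions arises during treatment:
- ALT or AST above 8×ULN;
- above 5×ULN, where it "persists for >2 weeks or based on clinical judgment of the investigator";
- above 3×ULN with total bilirubin above 2×ULN or INR above 1.5;
- above 3×ULN with listed symptoms or eosinophilia.

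**The retest rule.** For values above 3×ULN, Protocol 9.1.8 asks for follow-up tests "preferably within 48 to 72 hours and no later than 7 days after the abnormality was noted". If the value is still above 3×ULN, "the investigator must contact the Medical Monitor for consideration of additional testing, close monitoring, possible discontinuation of study drug".

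**The concern.** Each subject receives one dose per period. After Period 1, the only dose left to stop is the Period 2 dose, so item 23 and 7.5 bear on the same act although their numbers differ widely. Take an isolated ALT of 4×ULN on Study Day 8. Item 23 bars the subject. No limit in 7.5 is met, and 9.1.8 leads to a retest and a discussion. At the preferred interval that retest would come after the scheduled second dose.

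The surrounding text adds to the doubt. The lead-in to 7.2 is about qualifying for entry, and 7.0 wants all entry criteria confirmed before randomization. The inclusion/exclusion row of Appendix A is marked only at Screening and Period 1 Check-in. If two investigators could read the text and act differently on the same liver result, the stake would be subject safety first, and the loss of a fed/fasted pair second.

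**Working it through.** **1. Is it one sample?** Table 9.f gives 126 mL for clinical laboratory blood at 21 mL per sample. The count is Screening 1, Day -1 in two periods, Day 3 in two periods, and Day 8 in Period 2 only: 21 × (1 + 2 + 2 + 1) = 21 × 6 = 126 mL, as stated. A separate Period 1 Day 8 sample would give 21 × 7 = 147 mL. The Study Day 8 result is therefore both a post-dose value and a check-in value, and the overlap is real.

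**2. What does each rule say about an isolated value on that day?** (No bilirubin or INR rise, no symptoms, no persistence.)

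| ALT or AST, ×ULN | 7.2 item 23 | 7.5 item 1 | 9.1.8 retest | Any text that permits or requires the dose |
|---|---|---|---|---|
| up to 1.5 | not met | not met | no | not applicable |
| above 1.5 to 3 | bars | not met | no | none |
| above 3 to 5 | bars | not met | yes | none |
| above 5 to 8 | bars | stop on investigator judgment | yes | none |
| above 8 | bars | stop | yes | none |

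In the band above 1.5 to 8×ULN one rule applies, and the other is silent or discretionary. A contradiction would need a row where one passage forbids the dose and another permits or requires it. There is none.

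**3. Do the rules do the same work?** No. Item 23 is tested at named check-ins. Section 7.5 applies throughout treatment, and 9.1.8 also covers results after the second dose. A Study Day 3 value above 8×ULN that falls to 1.5×ULN or less by Study Day 8 meets 7.5 but not item 23. Neither rule makes the other redundant.

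**4. Does the calendar force a conflict?** On Appendix A the doses fall on Study Days 1 and 9, 9 − 1 = 8 days apart. The first post-dose laboratory sample is on Study Day 3, 9 − 3 = 6 days before the second dose. Persistence for more than 14 days therefore cannot be shown before that dose. Amendment 01 added the investigator-judgment wording for abnormalities of shorter duration, so this limb is not empty. A retest of a Study Day 8 value falls on Study Days 8 + 2 = 10 to 8 + 3 = 11 at the preferred interval, and on 8 + 7 = 15 at the latest. But 9.1.8 sets no minimum interval, and the washout of 7 days or more is a floor, so Study Day 9 is nominal. The retest date does not imply that the dose goes ahead first.

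**5. What would a withheld dose cost the primary analysis?** Inputs: intrasubject CV 37.5% for Cmax (Protocol 13.3, SAP 6.0), so the within-subject log SD is √ln(1 + 0.375²) = 0.3627. With equal sequences, half-width = t(0.95, n − 2) × 0.3627 × √(2/n). For 8 and 7 subjects, √(2/n) becomes √[½(1/8 + 1/7)].

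| Complete pairs | Half-width (ln scale) | 90% CI if the observed ratio is 2 |
|---|---|---|
| 16 | 0.226 (the plan's 0.23 after rounding) | 1.596 to 2.507 |
| 15 | 0.235 | 1.581 to 2.530 |
| 14 | 0.244 | 1.566 to 2.554 |

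One withheld dose adds 0.235 − 0.226 = 0.009 to the half-width.

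**The case for a change.** The best case for a change does not need a strict contradiction. It is that the text never says what follows when a subject fails a check at Period 2 Check-in. Besides the headings and the Appendix A row, 7.5 item 2 is the category for entry-criterion failures found after randomization, and it applies only where continuing poses an unacceptable risk. Section 7.6 ties the investigator's power to discontinue a subject to the 7.5 criteria. A site working from the Appendix A row might not apply item 23 on Study Day 8, while a site working from item 23 would.

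That gap exists. It is shared by seven criteria: 12, the cotinine sentence of 16, and 19 to 23. But to give the second dose despite a value above 1.5×ULN, a reader would have to disregard an explicit mention of Period 2 and the no-exemptions sentence in 14.2. Section 9.3.2 also describes eligible subjects being admitted at Check-in of each period. The urine drug screen, ECG, vital signs and laboratory tests needed for these checks are all scheduled for that visit. The eCRF category Other (7.5 item 8) can record the reason, and 7.6 allows replacement case by case. The consequence, no second dose, can be inferred without new text, and it is inferred in the same way for all seven criteria.

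**Conclusion.** The concern does not hold as a contradiction. The thresholds differ because one set is a check before a dose and the other governs stopping and follow-up. No ALT/AST value exists at which one passage forbids the second dose and another permits or requires it. What is left is a wording gap about the status of checks made after the first dose. A site or analyst fills it from the text already there.

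Stating the consequence outright would alter no endpoint, analysis set or estimate. The documents give no rate of such elevations, so an expected number of withheld doses cannot be calculated. Each one costs a single pair, about 0.009 on the log half-width for the first, and two dropouts are already allowed for.

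This rests on two assumptions: that item 23 is applied at Period 2 Check-in as written, and that the absence of a mandatory stop in 7.5 is not read as leave to dose. Which liver limits are clinically suitable is for the sponsor's clinical team, and nothing here takes a position on it.

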7.3 Excluded Medications, Supplements, Dietary Products

Use of the agents listed in [Table 7.a](#) is prohibited from the time points specified until completion of all study-related activities, including the Follow-up Phone Call.

Table 7.a Excluded Medications, Supplements, and Dietary Products

28 Days Prior to Check-in (Day -1) of Period 1	7 Days Prior to Check-in (Day -1) of Period 1	72 Hours Prior to Check-in (Day -1) of Period 1
Prescription medications (including hormone replacement therapy)	OTC medications (a)	Caffeine- or xanthine-containing products
Nutraceuticals (eg, St. John's wort, ginseng, kava kava, ginkgo biloba, Chinese herbs, and melatonin)	Vitamin supplements	Poppy seeds
Immunization/vaccines (b)	Foods or beverages containing grapefruit or grapefruit juice, star fruit or star fruit juice, Seville-type (sour) oranges or marmalade, apple juice, orange juice, pineapple juice, vegetables from the mustard green family (eg, kale, broccoli, watercress, collard greens, kohlrabi, Brussels sprouts, mustard), and charbroiled meats	
Nicotine-containing products	Alcohol-containing products	
Intake of known OTC inhibitors/inducers of CYPs 3A4/5, 2C9, 2C19, 2D6, 1A2, 2B6, 2E1, and 2A6 (c)		

CYP=cytochrome P-450, OTC=over-the-counter.

(a) Occasional use of acetaminophen (≤ 1 g/day) or other medication as approved by Takeda on a case-by-case basis is allowed.

(b) Inclusive of but not limited to H1N1 and other influenza vaccinations.

(c) Omeprazole, lansoprazole, cimetidine, ranitidine, and chlorpheniramine.

Subjects must be instructed not to take any medications, including OTC products, without first consulting with the investigator.

7.4 Diet, Fluid, Activity Control

Subjects will be confined to the clinic from Check-in (Day -1) through completion of study procedures on Day 3 in each period.

During each confinement period, subjects will be served standardized meals (except for Ensure Plus) and an evening snack, each containing ~30% fat (relative to total calories), and no additional food or drink (except for Ensure Plus for Regimen B and water for both regimens) will be allowed. For each regimen, the meals served on the day of dosing (Day 1) should be identical for all subjects. The study menu should be recorded and submitted to the study file with a copy provided to the sponsor before the start of the study. The meal start and stop times and the amount consumed will be recorded in the source document and appropriate electronic case report form (eCRF) page for the Day -1 snack and all meals (including Ensure Plus) served on Day 1.

For each regimen, TAK-831 will be administered on Day 1 after an overnight fast of ≥ 10 hours. For Regimen A (fasted state), subjects will be orally administered TAK-831 with 240 mL of water.

For Regimen B (fed state), subjects will start consuming Ensure Plus 15 minutes before oral administration of TAK-831. Ensure Plus is a nutritional drink of 237 mL (8 fl oz) and has 355 total calories. Of the total calories, 103 calories are from fat, with the total fat content (11 g) being 17% of the daily value based on a 2000 calorie diet; 52 calories are from protein, with the total protein content (13 g) being 26% of the daily value based on a 2000 calorie diet; and 201 calories are from carbohydrate, with the total carbohydrate content (51 g) being 17% of the daily value based on a 2000 calorie diet. Subjects should complete the Ensure Plus in 15 minutes or less; TAK-831 should be administered with 240 mL of water 15 minutes after the start of this meal. For each regimen, subjects will fast for an additional 4 hours after dosing. Subjects will be allowed to consume water ad libitum except for 1 hour before dosing and 1 hour after dosing.

For each regimen, subjects will not receive breakfast on Day 1 (dosing day). Lunch will be served 4 hours after dosing (after the 4-hour PK and PD blood sample collections), dinner ~9 hours after dosing, and a snack ~12 hours after dosing (after the 12-hour PK and PD blood sample collections). No meals will be served after the snack. Subjects will be fasting for ≥ 10 hours before collection of blood samples for clinical laboratory tests (except for those collected at Screening).

If a blood draw or any other study procedure coincides with a meal, the blood draw will take precedence, followed by the study procedure, and then the meal.

Foods and beverages that are prohibited during the study are listed in [Table 7.a](#).

Subjects will remain upright (seated, standing, or ambulatory) for 4 hours after dosing, except as necessitated by the occurrence of an adverse event (AE) or study procedures (eg, obtaining 12-lead ECG). Subjects will refrain from strenuous and/or unaccustomed exercise throughout the entire study until Study Exit.

